The recently published results of van den Elsen et al (31) reporting null effect of 1.5mg THC TID (4.5mg QD) suggest that if THC is to be effective for Agit-AD, this dose is too low. We observed benefit in our observational data with twice daily dosing for a mean total of 7mg QD, but the retrospective, uncontrolled study design did not allow a fine-grained look at dose effectiveness. Our preliminary data in younger adults suggests that an acute dose of 10 mg produces mild to moderate positive subjective effects with few adverse effects whereas higher doses do not increase positive subjective effects and are associated with cognitive impairment and mild-moderate AEs. Because our target population is frail and likely to be more sensitive to drug effects, we believe that a targeted 10 mg (5mg BID) daily dose will maximize both efficacy and maintenance of safety. The half-life of dronabinol is ~ 4 hours. [name] is a consultant on the study at Johns Hopkins who specializes in pharmacologic research on controlled substances including THC. Although [name] work in younger persons demonstrates subjective effects last 6-8 hours total; we propose to dose 6 hours apart to maximize daytime coverage for agitation, with dosing at 8 a.m. and 2 p.m. The morning dose is standardly used in our clinical practice; the afternoon dose is timed to target late-afternoon/early evening agitation, a very common cycle in Agit-AD (often inappropriately termed "sundowning"). [name] M.D. will also serve as a consultant on the study. [name] is a national expert on marijuana treatment and policy.

Outpatient Enrollments and Remote Assessments:

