- 2) Sponsor-Investigator will notify the FDA of the SAE and a report will be submitted to the Regulatory Project Manager (RPM)/ FDA reviewing division within 7 calendar days via telephone, fax or email
- 3) Following the Sponsor-Investigator's initial receipt of the SAE, any relevant observations from animal or epidemiological studies suggesting significant risk to human subjects will be reported within 15 calendar days to the FDA in a written Safety Report via MedWatch Form 3500A
- 4) Any relevant additional information obtained by the Sponsor-Investigator that pertains to the previously submitted Safety Report will be submitted as a Follow-up Safety Report, within 15 calendar days following the Sponsor-Investigator initially receiving the information

- Collection of vital signs
- General medical health rating (GMHR) (50): this is a valid and reliable 4-point global rating of the severity of medical co-morbidity in patients with AD that our center has used in previous AD trials (51,52)
- Adverse events monitoring: All adverse events occurring after randomization will be recorded. AEs will be assessed by using all available data to determine if new symptoms or medical events have occurred
- Observation of ECG changes
- Observation of changes in laboratory values.
- Neurological and physical Exams

Rationale for duration:

The average length of inpatient stay in our observational data was ~16 days, and to cover this time period 3 weeks should be sufficient. Additionally, in CitAD we observed that the placebo response largely reached its maximum after 3 weeks. We are proposing a trial of dronabinol for patients with Agit-AD; there are practical and ethical limitations on the duration of such a trial given available resources and the ongoing stress that families and caregivers are experiencing. If we demonstrate efficacy, there will likely be a role for dronabinol as a relatively rapidly acting agent for Agit-AD; for example, the full response to citalopram in CitAD was observed after 9 weeks (53). More rapid response should be beneficial for reducing family/caregiver stress. Since placebo response is largely complete by 3 weeks, we argue that 3 weeks will be sufficient to distinguish drug from placebo response and to address whether dronabinol achieves a rapid response in that timeframe.

Protocol: Pilot trial of dronabinol adjunctive treatment of agitation in Alzheimer's disease (AD) (THC-AD)

Protocol Number: IRB00052955

Protocol Version: 6.0/2July2020

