Medical History	X				
Other Medications	X				
Randomization		X			
Study medication dispensing		X	X	X	
Coronavirus Impact Scale (CIS)		X			
Unblinding*					X *
Clinical Instruments					
Pittsburgh Agitation Scale (PAS)		X	X	X	X
Neuropsychiatric Inventory, Clinician Version (NPI-C)		X	X	X	X
Cohen-Mansfield Agitation Inventory (CMAI)		X	X	X	X
Modified Alzheimer's Disease Cooperative Study- Clinical Global Impression of Change (CGI-C)		X	X	X	X
Alzheimer's Disease Cooperative Study - Activities of Daily Living (ADCS-ADL)		X	X	X	X
Confusion Assessment Method (CAM)		X	X	X	X
Sleep Assessment (NPI-C Sleep Subscale)		X	X	X	X
Cognition					
SIB-8		X			X
Mini Mental State Exam (MMSE)		X			X
Drug Effect					
Drug Effect Questionnaire (DEQ)		X	X	X	X
Medication Side-Effects Questionnaire		X	X	X	X
Safety and AE monitoring					
Physical Exam	X				
Neurological Exam	X				
Vital Signs		X	X	X	X
General Medical Health Rating (GMHR)	X				
Adverse Event Monitoring		X	X	X	X
ECG		X			X
Blood draw (DNA, Biomarker, CBC, CMP, TSH)		X			X

*Only done after all other study procedures are complete

Protocol: Pilot trial of dronabinol adjunctive treatment of agitation in Alzheimer's disease (AD) (THC-AD)

Protocol Number: IRB00052955

Protocol Version: 6.0/2July2020

6. **Biostatistical Analysis:**

All analyses will be conducted using STATA (55) and R (56) under the supervision of the study statistician ([name]). Descriptive analyses will be conducted and measures checked for outliers and to ensure that distributional assumptions of the planned analyses are appropriate. If not, analogous non-parametric methods will be used. Analyses will be intent-to-treat. We expect minimal missing data, but if there is a significant amount of missing data, multiple imputation may be used if appropriate (57). To investigate sensitivity to missing values, those with and without missing values will be compared by background covariates. Tests will be two-sided and p-values <0.05 will be considered significant.

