Multiple test corrections will be applied as appropriate. All primary analyses will be adjusted for site as well as the variables balanced through minimization (use of antidepressants and use of antipsychotics). To account for the inclusion of multiple sites, we will include site as a covariate, with individuals being seen on an outpatient (largely remote) basis being treated as its own site. Secondarily, we will fit models with site, site x time, and site x treatment x time to determine if there are any effects of site on treatment effect over time. These analyses must be secondary as the study was not powered to detect these 3 way interactions. Importantly, no participants were stopped during their participation and all participants will have the same mode of assessment (either in-person or remote) throughout.

Aim 1: Efficacy will be assessed by fitting a longitudinal linear model with the co-primary outcomes (PAS and NPI-C Agitation/Aggression/Sum of Agitation and Aggression) and with time, treatment assignment and interaction between time and treatment. The latter term will be the coefficient of interest and will represent the mean difference in change over the 3-week period between the treated and placebo groups. Within-person correlations will be handled via the method of generalized estimating equations (58).

Aim 2: We will model risk of a severe adverse event as a function of treatment assignment using logistic regression, and counts of total adverse events using ordinal logistic regression or poisson regression as appropriate. We will also scrutinize counts of each specific type of AE as a function of treatment assignment to determine if there are specific adverse events which we should power ourselves to detect in future larger-scale trials. Special attention will be paid to new-onset delirium, seizures, and arrhythmias. Additionally we will specifically look at the effect of dronabinol on cognition using the SIB-8, and a regression model analogous to that in Aim 1. We will stratify adverse events by site and assess whether rates of particular AEs vary by site. In particular, we will assess whether outpatients differ in their rates and types of AEs (either favorably, due to being less acute, or unfavorably, due to a less controlled environment where falls might be more likely, for example).

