Secondary Analyses: We will model change in additional outcomes (e.g., CMAI, MMSE, sleep, DEQ) using models analogous to that of Aim 1. We will also look at predictors of dronabinol response, including cannabinoid receptor polymorphisms and other patient characteristics. We will also model change in IL1 β , TNF α , and IL6 as a function of treatment assignment. All secondary analyses will be conducted with site as a covariate, and additional analyses which include site x treatment and site x treatment by time will be performed.

Sample size and Power analysis

Protocol: Pilot trial of dronabinol adjunctive treatment of agitation in Alzheimer's disease (AD) (THC-AD)

Protocol Number: IRB00052955

Protocol Version: 6.0/2July2020

We observed a large effect in our observational study that used PAS as outcome. PAS is one of the co-primary outcomes and we will estimate power to detect change in PAS. There are no pilot data to estimate power to detect change in NPI-C which has not been used in prior trials of dronabinol. The PAS declined in our observational study from 9.68 (3.91) pre-treatment to 5.25 (4.17) post-treatment for a treatment effect of 1.1 and 45% reduction in PAS score.

We propose to use a more conservative estimate of 30% reduction in PAS score and calculated statistical power using the formulae of Jung and Ahn (59). A 30% reduction translates to decreasing from 9.68 PAS points to 7.26 points after 3 weeks, which means a slope of -0.81 points/week. This translates to an effect size of 0.206. It is essential to account for missing data including those from dropouts. Assuming first a missing data pattern that increases monotonically to 15% by week 3, with N= 80, a within-person correlation of 0.5 and an exchangeable correlation structure, we will have 80% power to detect a treatment effect of size 0.22, which translates to a decrease in PAS from 9.68 to 7.1 over 3 weeks; this is a 26.7% decrease. Assuming next a missing data pattern that increases monotonically to 30% by week 3, then with 80 people and a within-person correlation of 0.5 and an exchangeable correlation structure, we would have 80% power to detect a treatment effect of size 0.24, which translates to a decrease in PAS from 9.68 to 6.87 over 3 weeks; this is a 29.1% decrease. Thus, THC-AD is well-powered to detect a clinically plausible and conservatively estimate decrease in PAS which is a co-primary outcome.

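### The power section presents detectable drug-placebo differences as falls in PAS from baseline, which describe the dronabinol arm only if placebo is flat, so its well-powered and conservative conclusion is not supported as written

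*Combined protocol and SAP*

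**What the plan says.** Section 6, Biostatistical Analysis (Aim 1), makes the time-by-treatment term the coefficient of interest and says that it "will represent the mean difference in change over the 3-week period between the treated and placebo groups". Under Sample size and Power analysis, power for PAS comes from the Jung and Ahn formulae for comparing slopes under generalized estimating equations, "with N= 80, a within-person correlation of 0.5 and an exchangeable correlation structure". The detectable effects at 80% power are 0.22 (15% missing by week 3) and 0.24 (30% missing) for N=80, and 0.25 and 0.27 for N=60.

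Each effect is then turned into a fall from the baseline mean of 9.68. The first is given as one "which translates to a decrease in PAS from 9.68 to 7.1 over 3 weeks; this is a 26.7% decrease"; the others end at 6.87, 6.75 and 6.51. The planning target is a 30% reduction, printed as 9.68 to 7.26, a slope of -0.81 per week and an effect of 0.206. It is scaled down from the 45% pre-post fall (9.68 to 5.25) in the investigators' inpatient case series. The N=80 paragraph concludes that "THC-AD is well-powered to detect a clinically plausible and conservatively estimate decrease in PAS". The section states no placebo change.

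Section 5, Rationale for duration, argues: "Since placebo response is largely complete by 3 weeks, we argue that 3 weeks will be sufficient to distinguish drug from placebo response". Non-pharmacologic strategies for addressing Agit-AD, also in section 5, gives all participants individualised standard care for agitation, including DICE.

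**The concern.** The tested quantity is a difference between arms, but the reader is given a change from baseline. The two coincide for the dronabinol arm only if placebo stays at 9.68 for 3 weeks. The protocol's own argument for its duration, and the active care given to both arms, point the other way.

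The planning figure has a related gap. The 45% fall comes from 40 inpatients treated for 7 days alongside other psychotropics (section 1). The Rationale for dosing describes that work as uncontrolled: "the retrospective, uncontrolled study design did not allow a fine-grained look at dose effectiveness". That sentence is about dose, but it confirms that there was no comparator. The observed fall may therefore contain non-drug improvement. Scaling it to 30% is not the same as subtracting a placebo change, and the plan does not say that the 30% is net of placebo.

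At stake is how the result is read. A colleague using this section would conclude that a fall of about 27 to 29% on dronabinol is detectable with 80% power, and could weigh a null result accordingly.

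**Working it through.** **Inputs.** From section 6: two-sided alpha 0.05, 80% power, N=80 or 60, exchangeable correlation 0.5, missingness rising to 15% or 30% by week 3, baseline PAS 9.68 (SD 3.91). From section 4: allocation close to 1:1. Assumed: visits at weeks 0, 1, 2 and 3, and monotone missingness in equal weekly steps.

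**Step 1: reproduce the detectable effects.** With p_j the proportion observed at week t_j:

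- τ = Σp_j t_j / Σp_j
- A = Σp_j(t_j − τ)²
- V = ΣΣ p_jk ρ_jk (t_j − τ)(t_k − τ), with p_jk = min(p_j, p_k)
- SE of the slope difference, in SD per week = √[V / (N × 0.5 × 0.5 × A²)]
- Detectable effect = (1.960 + 0.842) × SE

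For 15% missing, p = 1, 0.95, 0.90, 0.85, so τ = 5.30/3.70 = 1.432, A = 4.608 and V = 2.515. At N=80, SE = √[2.515/(20 × 4.608²)] = 0.0770.

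For 30% missing, p = 1, 0.90, 0.80, 0.70, so τ = 4.60/3.40 = 1.353, A = 4.176 and V = 2.502. At N=80, SE = 0.0847.

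For N=60, multiply each SE by √(80/60).

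| N, missing | Recomputed | Stated | Stated × 3.91 × 3 weeks | 9.68 minus this | Printed |
|---|---|---|---|---|---|
| 80, 15% | 0.216 | 0.22 | 2.58 points | 7.10 | 7.1 |
| 80, 30% | 0.237 | 0.24 | 2.82 | 6.87 | 6.87 |
| 60, 15% | 0.249 | 0.25 | 2.93 | 6.75 | 6.75 |
| 60, 30% | 0.274 | 0.27 | 3.17 | 6.51 | 6.51 |

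All four effects are reproduced as between-arm slope differences. The printed end scores arise by subtracting the whole between-arm difference from one baseline.

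**Step 2: power when placebo moves.** The SE of the 3-week difference at N=80 is 0.0770 × 3.91 × 3 = 0.903 points (15% missing) or 0.0847 × 3.91 × 3 = 0.993 (30% missing). Power = Φ(D/SE − 1.96), where D is the drug-placebo difference. A 30% fall is 0.30 × 9.68 = 2.90 points. The placebo falls below are assumptions.

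*30% read as dronabinol's total fall (D = 2.90 minus the placebo fall), N=80:*

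| Assumed placebo fall | D | Power, 15% missing | Power, 30% missing |
|---|---|---|---|
| 0% | 2.90 | 90% | 83% |
| 10% (0.97 points) | 1.94 | 57% | 50% |
| 20% (1.94 points) | 0.97 | 19% | 16% |

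On this reading, power falls below 80% once placebo falls by more than about 3 to 4% (15% missing) or 1% (30% missing).

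*30% read as a net difference (D = 2.90 whatever placebo does):* 90% with 15% missing and 83% with 30% missing.

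*Dronabinol repeats the full observed fall, 9.68 − 5.25 = 4.43 points:* with 15% missing, 80% power is kept up to a placebo fall of 4.43 − 2.58 = 1.85 points (19%), or 4.43 − 2.53 = 1.90 (20%) with the unrounded effect (0.2156 × 3.91 × 3 = 2.53).

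**Step 3: the printed target.** (9.68 − 7.26)/9.68 = 2.42/9.68 = 25.0%, not 30%. Its slope of 2.42/3 = 0.81 per week, divided by 3.91, gives the printed 0.206. A true 30% fall ends at 9.68 − 2.90 = 6.78, with effect 2.90/(3 × 3.91) = 0.248. The printed 0.206 lies below both N=80 detectable effects. Its power at N=80 is Φ(0.206/0.0770 − 1.96) = 76% with 15% missing and 68% with 30% missing, even with flat placebo.

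**The case against.** The strongest reply is that the calculation is already between-arm. The model tests the difference in change, the formula compares slopes, and the power for a slope difference does not depend on the placebo slope. This stands. A reader might infer from the matching end scores that the power calculation itself assumes a flat placebo arm; it does not. Only the translation into PAS scores carries that implication.

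Second, the 30% can be defended as a net difference. Cutting 4.43 points to 2.90 leaves 1.53 points (16% of baseline) for placebo and natural improvement, and 30% exceeds both N=80 thresholds (26.7% and 29.1%). This is arithmetically sound, and on that reading the 57% and 19% powers would subtract placebo twice. But the plan calls the 30% a reduction in PAS score and nowhere says that it is placebo-subtracted. The defence also does not rescue the printed 0.206.

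Third, a reader might infer that any realistic placebo response leaves the trial underpowered. The documents do not support this. They give the timing of the placebo response, not its size, and the timing comes from the earlier citalopram trial, whose participants were largely outpatients and which excluded severe agitation and antipsychotic users (section 1).

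Finally, this is a pilot whose analysis will estimate the between-arm difference directly, so the misreading concerns the power statement and not the estimate. That limits the severity.

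**Conclusion.** Wrong as written, of moderate severity. The detectable effects are correct as drug-placebo differences of about 2.58 and 2.82 PAS points at N=80, and 2.93 and 3.17 at N=60. Their description as falls from 9.68 is true of dronabinol patients only if placebo does not change, which conflicts with the stated rationale for duration.

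The claim to be well powered and conservative is not established. It depends on an unstated choice between two readings of 30% and on a placebo change that is nowhere given. Independently of placebo, the printed target has less than 80% power at N=80 under both missing-data patterns, and at N=60 the plan's own detectable falls (30.3% and 33%) already exceed 30%.

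These results rest on the protocol's SD of 3.91 and correlation of 0.5, on equal-step missingness, and on assumed placebo falls. They do not show that the sample size or duration must change, nor that the trial is underpowered against its true effect, which is unknown.

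**What to change.** In Sample size and Power analysis:

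1. Replace each one-arm translation with the placebo-subtracted difference in 3-week PAS change: about 2.58 and 2.82 points at N=80, and 2.93 and 3.17 at N=60.
2. State whether the 30% is a net difference or dronabinol's total fall, and the placebo change assumed. If no placebo figure is available, show a range.
3. Make 30%, 7.26 and 0.206 agree: 30% gives 6.78 and an effect of about 0.25; 7.26 is 25% with 0.206.
4. Replace the well-powered and conservative conclusion with the power that follows from items 2 and 3.

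The cost is protocol wording and a possibly less favourable stated power. Sample size, duration, treatment and the analysis model are unchanged.

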Medication Side-Effects Questionnaire		X	X	X	X
Safety and AE monitoring					
Physical Exam		X			
Neurological Exam		X			
Vital Signs		X	X	X	X
General Medical Health Rating (GMHR)	X				
Adverse Event Monitoring		X	X	X	X
ECG		X			X
Blood draw (DNA, Biomarker, CBC, CMP, TSH)		X			X

*Only done after all other study procedures are complete.

Outpatient Enrollment – Procedures Color Legend:	
Completed in-person	
Completed remotely via HIPAA compliant video software	
Completed via optional location (in-person or remote)	

Unmasking:

Every effort will be made to maintain the masked nature of the trial while taking precautions to optimize participant safety. Unmasking of treatment assignment before 3 weeks (“emergency unmasking”) will be limited to medical situations in which withholding knowledge of the identity of the drug will lead to unreasonable danger or suffering, and will not be necessary for routine management of potential side effects. The Research Pharmacy will have 24-hour access to treatment unmasking information. In an emergency situation, the study physician may elect to unmask a participant’s treatment assignment. All participants will undergo treatment unmasking at the endpoint of the study. This will either be at the Week 3 visit, or earlier if study treatment is discontinued prior to the third week. Participants and their referring physicians will be informed of treatment assignment after unmasking.

5. Participant Procedures:

Following the informed consent process, each participant will complete assessments conducted by the study coordinator and the principal investigator or delegated study staff member. The specific assessments conducted are detailed below. The participant’s participation will be comprised of 4 visits spanning their 3-week study enrollment. The study procedures per visit are outlined in Table 2.

- **Coronavirus Impact Scale (CIS):** The CIS is a short, 12-item scale that rates the influence of the Coronavirus (COVID-19) pandemic on multiple health factors, including employment, access to healthcare, and stress. The CIS was developed by [name] MAS, and [name].

Clinical Assessments

- **Pittsburgh Agitation Scale (PAS) (40) (Co-primary outcome):** The PAS was developed for both

Protocol: Pilot trial of dronabinol adjunctive treatment of agitation in Alzheimer’s disease (AD) (THC-AD)
Protocol Number: IRB00052955 **Protocol Version:** 6.0/2July2020

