We repeated the above power analysis assuming a sample size of 60 in the event that we do not meet our original recruitment goals. With a missing data pattern that increases monotonically to 15% by week 3, with N=60, a within-person correlation of .5 and an exchangeable correlation structure we will have 80% power to detect a treatment effect of size .25, which translates to a decrease in PAS from 9.68 to 6.75 over 3 weeks; this is a 30.3% decrease. With a missing data pattern that increases monotonically to 30% by week 3, and identical conditions otherwise, we would have 80% power to detect a treatment effect of size .27, which translates to a decrease in PAS from 9.68 to 6.51 over 3 weeks; this is a 33 % decrease.

7. Risks and Discomforts:

Study medication side effects:

Based on the list of potential side effects from clinical trials with dronabinol, items will include nausea, diarrhea, dry mouth, upset stomach, vomiting, vivid or abnormal dreams, anxiety, dizziness, fatigue, confusion, depersonalization, hallucination, paranoia, depression, rapid heart rate/palpitations, flushing in the face or body, tinnitus, speech difficulty, blurred vision, headache, sweating, runny nose, and coughing.

Potential substance abuse:

Dronabinol is a Schedule III substance indicating moderate abuse liability relative to other drugs. Given the low doses to be administered, close monitoring of participants and medication administration, and relatively short duration of exposure proposed in the present study, we believe the risk of participants misusing the study medication or becoming dependent on dronabinol to be very low. Outcomes obtained from the DEQ patient-based and informant-based questionnaires will provide outcomes relevant to examining the abuse liability of the study doses in this population (e.g. subjective ratings of pleasant drug effect) that will be valuable for future studies. We will also evaluate whether participants or families of non-responders to dronabinol request to continue medication after the trial is completed.

Protocol: Pilot trial of dronabinol adjunctive treatment of agitation in Alzheimer's disease (AD) (THC-AD)

Protocol Number: IRB00052955

Protocol Version: 6.0/2July2020

Risk of Treatment Limitations:

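### The supplementary continuation-request item is limited to dronabinol non-responders, has no placebo comparator, and may be influenced by knowledge of the assignment

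*Combined protocol and SAP*

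**What the plan says.** Section 7, Potential substance abuse, names two sources of information. The first is the DEQ in its patient and informant versions, which "will provide outcomes relevant to examining the abuse liability of the study doses in this population". The second is added in the next sentence: "We will also evaluate whether participants or families of non-responders to dronabinol request to continue medication after the trial is completed".

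Section 6, Secondary Analyses, covers the DEQ: "We will model change in additional outcomes (e.g., CMAI, MMSE, sleep, DEQ) using models analogous to that of Aim 1". The Aim 1 model is fitted "with time, treatment assignment and interaction between time and treatment", so the DEQ is compared between arms. Section 6 does not mention continuation requests. Neither visit table (Table 1 for outpatients, Table 2 for the study generally) lists a continuation question, and the documents do not define a non-responder.

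On timing, the Unmasking paragraph in section 4 says: "All participants will undergo treatment unmasking at the endpoint of the study". It continues: "This will either be at the Week 3 visit, or earlier if study treatment is discontinued prior to the third week". It then adds: "Participants and their referring physicians will be informed of treatment assignment after unmasking". In both visit tables the footnote to the Week 3 unblinding entry reads "Only done after all other study procedures are complete".

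**The concern.** A wish to keep taking a drug that did not help points to drug liking only if it is more common than the same wish among people who took placebo without benefit. Families of severely agitated patients may ask to continue any study medication, out of hope or for lack of alternatives. As written, the item would not record that background rate.

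Timing adds a second difficulty. Families who ask after unmasking know whether the participant received dronabinol, and that knowledge may prompt or deter the request.

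The stakes are modest. The item is a remark in the risk section and enters neither the primary analysis nor any listed secondary outcome. But the sponsor chose to collect it, and it is the only request-based measure in the paragraph. Section 5 concedes that evidence on the DEQ's validity and reliability in cognitive impairment is limited, so a second measure is worth having if it can be interpreted.

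**Working it through.** The documents give no rate, count or power for continuation requests, so there is no figure to reproduce. The check is mainly a comparison of texts, with arithmetic for scale.

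**Step 1: the two measures side by side**

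| | DEQ | Continuation request |
|---|---|---|
| Who | All participants, both arms | Dronabinol non-responders only |
| When | Baseline and Weeks 1, 2 and 3 (Tables 1 and 2) | Not in either table |
| Masked | At Week 3 yes, because unblinding follows all other procedures | Not stated |
| Analysis | Aim 1-type model with treatment and time-by-treatment terms | None given |

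The gap therefore lies in the second measure only.

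**Step 2: before or after disclosure?** Section 7 refers to the time after the trial is completed. That phrase can date the request, which would then follow disclosure under section 4. It can also describe the period for which medication is wanted; a family could then ask at Week 3 while still masked, with the assignment used later only to classify the case. The text does not settle which is meant.

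**Step 3: size of the denominator**
- 80 randomized (section 3) at close to 1:1 (section 4) gives about 40 on dronabinol.
- Non-response is assumed at 35% to 60%. The ends come from section 1: 65% improved in the dronabinol chart review (100 − 65 = 35), and about 40% responded in the citalopram trial (100 − 40 = 60). Neither is an estimate for this trial.
- 40 × 0.35 = 14 and 40 × 0.60 = 24. With the fallback sample size of 60 in section 6, about 30 per arm, 30 × 0.35 ≈ 10 and 30 × 0.60 = 18.

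**Step 4: precision of a one-arm count** (exact binomial, two-sided 95%)
- No requests: the upper limit is 1 − 0.025^(1/n), which is 23% for n = 14 and 14% for n = 24.
- About 30% requesting (assumed): 4/14 gives 8% to 58%; 7/24 gives 13% to 51%.

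These widths reflect small numbers. They are not evidence of bias.

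**Step 5: what a placebo comparison could detect.** Assume a placebo request rate p1 = 0.10, two-sided alpha 0.05 and n per arm. The normal approximation is

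power = Φ{[(p2 − p1) − 1.96 × SE0] / SE1}, where SE0 = √[2 p̄(1 − p̄)/n], SE1 = √{[p1(1 − p1) + p2(1 − p2)]/n} and p̄ = (p1 + p2)/2.

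For n = 40 and p2 = 0.36: p̄ = 0.23, SE0 = √(2 × 0.23 × 0.77/40) = 0.0941, and SE1 = √[(0.09 + 0.2304)/40] = 0.0895. Then (0.26 − 1.96 × 0.0941)/0.0895 = 0.84, and power = 0.80.

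| Comparison | Dronabinol request rate needed for 80% power |
|---|---|
| All participants, 40 vs 40 | about 36% |
| Non-responders, 24 vs 24 | about 46% |
| Non-responders, 14 vs 14 | about 59% |
| All participants, 30 vs 30 | about 41% |
| Non-responders, 18 vs 18 | about 52% |
| Non-responders, 10 vs 10 | about 68% |

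The non-responder rows assume equal numbers in the two arms. The approximation is rough at the smallest sizes, but the message is clear: only a large difference could be detected.

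**The case against.** The strongest reply is that drug liking is already measured properly. The DEQ is collected in both arms, precedes unmasking at Week 3 and is modelled by treatment. A reader might infer from the continuation sentence that the trial's abuse-liability assessment has no placebo comparison. The documents do not support that, and this part of the reply stands.

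Three other stronger readings also fail.
- **The trial will judge abuse liability from this item.** The abuse-liability wording belongs to the DEQ sentence. The continuation item is linked to it by heading and position, with no test or decision attached.
- **Requests are counted only after unmasking.** This is one reading of an ambiguous phrase (Step 2).
- **The item measures reaction to knowing the assignment.** At most, that knowledge may influence requests made after disclosure. Moreover, unmasking reveals the arm. The drug class is already known, since caregivers are told about the possible side effects of dronabinol.

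Two practical objections have some force. A prompted question is not the same as a spontaneous request, so the proposed change alters what is measured somewhat. And adding a placebo arm does not cure the small numbers.

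None of this supplies the missing comparator, the analysis or the definition of a non-responder.

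**Conclusion.** The point holds for the supplementary continuation-request item only. Followed as written, it yields a count in one arm and in an undefined subgroup, and cannot distinguish drug liking from an ordinary wish to continue treatment. If requests are made after disclosure, knowledge of the assignment may add to the difficulty; the text leaves the timing open.

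The importance is low. The primary analysis and the listed secondary outcomes are untouched, and the masked DEQ comparison remains. The numbers in the working rest on assumed non-response and request rates and show scale only. Even when corrected, the item would be descriptive.

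**What to change.** At Week 3, or at early stop, and before the assignment is disclosed, record for every participant in both arms whether the participant or family wishes to continue study medication. Use one fixed wording. The tables already place unblinding last at Week 3, so a masked window exists there; state that the same order applies when treatment stops early.

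Define non-responder once and apply the definition to both arms. Report the wish to continue by arm in two ways: overall, which is the randomized comparison, and within non-responders, which is a subgroup formed after randomization. Give counts and exact intervals beside the DEQ results, labelled descriptive. Spontaneous requests can be noted separately if that construct is of interest. The question records a wish only and implies nothing about treatment after the trial.

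The cost is one added question at an existing contact, one definition and one table. The drawbacks are the shift from spontaneous to prompted requests and the low precision.
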